8.1.3. Study Drug Dose Reductions or Discontinuation of Study Drug
In subjects who experience toxicity who cannot be ameliorated by the use of
adequate medical intervention, dose reductions can be performed. Patients
who experience a Grade 3 or greater toxicity considered to be related to
apalutamide that cannot be ameliorated by the use of adequate medical
intervention should have their treatment interrupted until the toxicity
improves to a Grade 1or baseline. Patients may subsequently be re-started
on study drug at a reduced dose as per the discretion of the Principal
Investigator. If study drug needs to be discontinued for more than 30 days
due to toxicities, the patient should be discontinued from the study treatment
phase, all pre-op visit procedures should be followed, and the patient
scheduled to undergo surgery as soon as recommended by medical team.

Apalutamide Dose Levels

Dose Level	Total Daily Dose	Number of 60 mg Tablets (QD)
0	240 mg	4
-1	180 mg	3
-2	120 mg	2

- 8.1.4. Medications—Drugs and Therapies
 - 8.1.4.1. Medication taken within four weeks prior to treatment initiation must be captured in the medical record. All concomitant medications will be documented at each visit while patient is taking apalutamide, and at the time of early study treatment discontinuation. Only adjuvant/salvage therapies will be documented during the follow-up phase of the study. Standard concomitant medications associated with surgery and post-op care will not need to be captured for the purpose of this study unless it is given to treat a reportable AE.
 - 8.1.4.2. No other new systemic therapy or new radiotherapy for treatment of prostate cancer is permitted while subject is on the active phase of study treatment or prior to surgery. Adjuvant/salvage therapies after surgery could be initiated if necessary at the discretion of the treating physician.
 - 8.1.4.3. As a class effect, AR antagonists have been associated with seizures due to an off-target mechanism of action (gamma amino butyric acid chloride channel [GABAA] inhibition). Drugs known to lower the seizure threshold or cause seizures are prohibited and a representative list is included below. A medication list review must be done by the clinical team if the patient is on medications from the below class list:
 - Atypical antipsychotics (e.g. clozapine, olanzapine, risperidone, ziprasidone)
 - Bupropion
 - Lithium
 - Meperedine and pethidine

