2015-0693 June 10, 2022 Page 36

The following methods are acceptable for transmission of safety information to Janssen Scientific Affairs. LLC:

 Electronically via Janssen SECURE Email service (preferred) - [contact]

Please use the contact information and process information provided by Janssen.

Abnormal Laboratory Results

The criteria for determining whether an abnormal laboratory test result should be reported as an adverse event are as follows:

- 1. Test result is associated with accompanying symptoms, and/or
- 2. Test result requires additional diagnostic testing or medical/surgical intervention (merely repeating an abnormal test, in the absence of any of the above conditions, does not meet criteria for reporting and an AE), and/or
- 3. Test result leads to a change in study dosing or death from the study, significant additional concomitant drug treatment or other therapy, and/or
- 4. Test result leads to any of the outcomes included in the definition of a serious adverse event, and/or
- 5. Test result is considered to be an adverse event by the investigator

Any abnormal test result that is determined to be an error does not require reporting as an adverse event, even if it did meet one of the above conditions except for condition #4. Clinically significant laboratory results must be recorded in the Department of Urology database.

Dose Modification/Toxicity Management

Subjects who experience a Grade 3 or greater toxicity considered to be related to apalutamide that cannot be ameliorated by the use of adequate medical intervention should have their treatment interrupted until the toxicity improves to a Grade 1 or baseline. Subjects may subsequently be re-started on study drug at a reduced dose follow a discussion between the Principal Investigator. Dose modifications are provided as guidance and should not replace the investigator's own clinical judgment.

[figure not shown]
Toxicity	Dose of JNJ-56021927 (assuming 240 mg/day dosing)
Grade 1 or 2	If a Grade 2 Toxicity has not resolved to Grade≤1 after 30 days, study drug will be discontinued. For all other Grade 1 or 2 Toxicities there will be no change.
(First Occurence) ≥Grade 3	Hold until Grade 1 or baseline, resume at full dose
First Recurrence ≥Grade 3	Hold until Grade 1 or baseline, resume at 180 mg (3 tablets)
Second Recurrence ≥Grade 3	Hold until Grade 1 or baseline, resume at 120 mg (2 tablets)
Third Recurrence ≥Grade 3	Discontinue

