First occurrence of seizure of any grade or Grade 4 neurotoxicity	Discontinue

Rash

Dose modifications for rash are allowed only for apalutamide and are summarized in below table. If the skin rash has any component of desquamation, mucosal involvement, or pustules, stop dosing with apalutamide, refer to dermatologist for evaluation, and a skin biopsy is recommended (in addition to the interventions listed in below Table) If the skin rash is Grade 3 or higher, asking the subject to consent to documentation by a photograph and further evaluation by a dermatologist should also be considered.

Severity	Intervention
Grade 1	 Continue apalutamide at current dose Initiate dermatological treatment^a Topical steroid cream AND Oral Antihistamines Monitor for change in severity^a
Grade 2 (or symptomatic Grade 1) ^b	 Hold apalutamide for up to 28 days Initiate dermatological treatment^a Topical steroid cream AND Oral Antihistamines Monitor for change in severity^a If rash or related symptoms improve, reinitiate apalutamide when rash is Grade≤1. Consider dose reduction at a 1 dose level reduction^c.
Grade ≥3 ^d	 Hold apalutamide for up to 28 days Initiate dermatological treatment^a Topical steroid cream AND Oral Antihistamines AND Consider short course of oral steroids Reassess after 2 weeks (by site staff), and if the rash is the same or has worsened, initiate oral steroids (if not already done) and refer the subject to a dermatologist Reinitiate apalutamide at a 1 dose level reduction^e when rash is Grade≤1.

2015-0693 June 10, 2022 Page 38

Note: Rash may be graded differently according to the type of rash and associated symptoms. For example, maculo-papular rash is graded by body surface area covered and not severity of the rash. Please consult NCI-CTCAE Version 4.03 for specific grading criteria for other types of rash.

- a Obtain bacterial/viral cultures if infection is suspected
- **b** Subject presents with other rash related symptoms such as pruritus, stinging, or burning
- **c** 1 dose level reduction = 60mg (1 apalutamide tablet)
- **d** If there is blistering or mucosal involvement, stop apalutamide dosing immediately and contact Janssen
- **e** If a subject previously started oral corticosteroids, continue for at least 1 week after resumption of reduced dose of apalutamide. If the proposed total oral steroid use will exceed 28 days, contact Janssen.

Criteria for Discontinuation of Study Treatment

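### For a first related Grade 3 or higher toxicity that treatment cannot ameliorate, the text names only a reduced restart dose while the table below it says full dose, and neither is stated to be the default

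*Combined protocol and SAP*

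**What the plan says.** Four places in the combined protocol and SAP bear on the restart dose.

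- **Section 8.1.3.** After a related Grade 3 or greater toxicity that medical intervention cannot ameliorate, drug is interrupted until Grade 1 or baseline. The patient may then be restarted "on study drug at a reduced dose as per the discretion of the Principal" Investigator. Three dose levels are listed: 240, 180 and 120 mg per day.
- **Section 8.2.4, Dose Modification/Toxicity Management, text.** The same condition is used: related toxicity that "cannot be ameliorated by the use of adequate medical intervention should have their treatment interrupted". It continues: "Subjects may subsequently be re-started on study drug at a reduced dose follow a discussion between the Principal Investigator". The sentence is incomplete and does not say who else joins the discussion. The text adds that the modifications are guidance and do not displace clinical judgment.
- **The table directly below that text.** For a first occurrence at Grade 3 or higher: "Hold until Grade 1 or baseline, resume at full dose". The first recurrence resumes at 180 mg, the second at 120 mg, and the third leads to discontinuation. For lower grades, apart from a Grade 2 toxicity unresolved after 30 days, it says "For all other Grade 1 or 2 Toxicities there will be no change".
- **The rash table, under its own Rash heading.** For Grade 3 or higher rash: "Reinitiate apalutamide at a 1 dose level reduction" once the rash is Grade 1 or less, with no distinction between first and later episodes. For Grade 2 or symptomatic Grade 1 rash: "Hold apalutamide for up to 28 days". A footnote sets one level at 60 mg.

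**The concern.** A clinician managing a first qualifying event finds a reduced dose in the text and full dose in the table on the same page. Nothing ranks one above the other. Two patients with the same event could restart on different daily doses with both courses consistent with the protocol.

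That is first a matter of consistent safety management. It also reaches the data. Safety and tolerability is a secondary objective (section 3.2.1). Counts of dose reductions and summaries of exposure would partly reflect which passage was followed rather than how the drug was tolerated, and a dosing deviation would be hard to define.

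**Working it through.** No sample size, power or error rate is involved, so the check compares the passages and does one subtraction.

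**1. Do the instructions cover the same patient?** The text requires three things: Grade 3 or higher, related to apalutamide, and not ameliorated by medical intervention. The table row requires only Grade 3 or higher and a first occurrence. The scopes are not identical, but any patient who meets the text's three conditions for the first time is also in the table row. The conflict lies in that overlap.

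**2. What restart dose does each give, starting from 240 mg per day?**

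| Source | First Grade 3 or higher event | Daily dose |
|---|---|---|
| Section 8.1.3 text | may restart reduced, at discretion | 180 or 120 mg (level not named) |
| Section 8.2.4 text | may restart reduced, after discussion | 180 or 120 mg (level not named) |
| Section 8.2.4 general table | resume in full | 240 mg |
| Rash table (rash only) | one level lower | 240 − 60 = 180 mg |

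**3. Size of the gap.** Smallest: 240 − 180 = 60 mg, and 60/240 = 25%. Largest, if the text were used to go down two levels: 240 − 120 = 120 mg, and 120/240 = 50%. Because the text names no level, 25% is a lower bound on the difference.

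**4. Does it carry through to stopping drug?** The Criteria for Discontinuation of Study Treatment stop drug when related toxicity needs more than two dose reductions. Under the general table the sequence is 240, 180, 120, stop, so drug stops at the fourth event (the third recurrence). If instead every qualifying event brought one reduction (an assumption, since the text does not fix the step), the sequence would be 180, 120, stop, and drug would stop at the third event. The two readings can therefore differ by one event on discontinuation.

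**5. Rash.** The general table has a separate row for seizure and Grade 4 neurotoxicity, but its Grade 1 or 2 row and its first Grade 3 or higher row do not exempt rash. Read literally, a Grade 2 rash is both held and left unchanged, and a first Grade 3 rash is both reduced one level and resumed in full. The separate Rash heading suggests the intended order, but no sentence states it.

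**6. What is not touched.** Section 6.2 makes a patient evaluable for the primary endpoint on at least 9 weeks of therapy plus prostatectomy, with no dose criterion, so the calculation of that proportion and its interval does not depend on the restart dose. Section 6.3 counts a TOX only if an adverse event prevents surgery or there is a treatment-related death before it.

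**The case against.** The strongest reply is that the text is permissive. Section 8.1.3 says that reductions can be made, both texts say that a patient may restart lower, and section 8.2.4 calls the modifications guidance. A permissive text can sit beside a table of defaults, and some variation in dose follows from stated discretion in a single-center trial. This stands to the extent that the text does not mandate a reduction. It does not remove the conflict: discretion allows departure from a default, but the protocol does not say that the table is the default, and the only restart dose the text mentions is a reduced one.

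Second, rash has its own heading and table, and a specific rule ordinarily prevails over a general one. This largely stands. A reader might infer a three-way contradiction for every Grade 3 or higher event. The documents do not support that: the rash table applies only to rash, and for other toxicities the conflict is text against general table. What remains for rash is a missing precedence sentence.

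Third, the safety stake has limits. All the instructions hold drug until recovery (Grade 1 or baseline; Grade 1 or less for rash), and none goes above the protocol dose of 240 mg.

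**Conclusion.** The inconsistency is real and narrow. It applies to a first related Grade 3 or higher toxicity that medical intervention cannot ameliorate. There the text points to a reduced dose and the table to full dose, at least 60 mg (25%) apart. This assumes the patient was on 240 mg, as the table itself does. The number of patients affected cannot be estimated from the documents.

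A reader might infer that the restart dose changes the TOX count, because section 6.3 says that men managed with dose reductions who proceed to surgery are not counted. That does not follow. A man who resumes at full dose and reaches surgery is not a TOX either. An effect would require the restart dose to change whether he reaches surgery, and the documents give no basis for that. Nor is the primary endpoint calculation affected. The consequence is inconsistent safety management and exposure and tolerability data that are harder to interpret. No view is taken here on which restart dose is right.

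**What to change.** - Reconcile the section 8.1.3 text, the section 8.2.4 text and the section 8.2.4 general table into one restart rule per event, using the same conditions (relatedness, response to medical intervention, first or recurrent event) in each place. Complete the unfinished sentence about the discussion with the Principal Investigator.
- Check the reconciled rule against the discontinuation criterion on more than two dose reductions, so that both give the same stopping point.
- Add one sentence stating whether the rash table or the general table governs rash, at Grade 2 as well as at Grade 3 or higher.

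The content of the rule is for the investigator and the drug supplier to decide. The cost is a protocol wording amendment, with no added patients, visits or data.

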9. CORRELATIVE STUDIES

The specimens collected in the context of this protocol are blood and tissue. These will be stored in a manner that will allow us to address the secondary aims in this protocol.

2015-0693 June 10, 2022 Page 40

Any future additional analyses not specified in this protocol will be agreed upon by prior approval from Janssen Scientific Affairs, LLC.

All specimens will be prospectively encoded with de-linked numbers such that the receiving lab will not have access to patient identifiers. Investigators involved in this project will ensure confidentiality of patients by restricting access to the GU Research Laboratory database in which the unique identification numbers cross-referenced to the MDACC patient medical record number will be kept. Clinical information will be accessed by investigators using the institutional electronic medical record, which stores clinical information and care reports of patients who are being treated at MDACC. Access to the MDACC electronic medical record is restricted with a security password. Any individual patient's information will not be reused or disclosed to any other person or entity, or for other research. All requests for use of this material must be in the context of IRB approved protocols.

